PRIMARY OBJECTIVE(S)	The primary objectives of this study are to assess 1) the safety and 2) efficacy of combining Anti-PD-1/PD-L1 blockade with palliative radiation therapy in patients with Stage IV Merkel Cell Carcinoma. Efficacy for the primary objective will be tumor response rates (CR, PR, SD, irCR, irPR, irSD) at both irradiated and unirradiated sites.
SECONDARY OBJECTIVE(S)	Assessment of Overall Survival and disease control rate/duration of response (CR, PR, SD, irCR, irPR, irSD).
EXPLORATORY OBJECTIVE(S)	Optional exploratory objectives (dependent upon funding) will include mutational burden/MSI analysis, measurement of polyomavirus in the blood, immune response assays at baseline, 2 weeks (± 1 weeks) and 8 weeks (± 1 weeks) after radiation therapy, and possible tumor biopsy studies.
TREATMENT SUMMARY	Pembrolizumab will be administered ~every 3 weeks for at least 4 cycles with palliative radiation administered between cycle 1 and cycle 2. Subjects will participate until disease progression or unacceptable toxicity. Participants will have an end of treatment visit 3 weeks (± 1 week) after the last dose of pembrolizumab and then follow up visits every 3 months (± 1 month) for two years and then every 6 months (± 1 month) for years 3-4, then again at year 5 (± 1 month) from the last dose of pembrolizumab or until disease progression. Follow Up visits will then become optional and SOC. After

	discontinuation of treatment, subjects will enter survival follow up conducted every 6 months (± 2 weeks) for 5 years from last dose of pembrolizumab.
SAMPLE SIZE	30 participants over 36 months
STATISTICAL CONSIDERATIONS	Data will be summarized using appropriate descriptive statistics: proportions with 95% confidence intervals, means, standard deviations, and ranges.

SCHEMA

LIST OF ABBREVIATIONS AND DEFINITION OF TERMS

AE	Adverse event
APC	Antigen presenting cell
CBC	Complete blood count
CI	Confidence interval
C _{MAX}	Maximum concentration of drug
CNS	Central nervous system
CRF	Case report/Record form
CR	Complete response
CTCAE	Common Terminology Criteria for Adverse Events
DLT	Dose Limiting Toxicity
DOR	Duration of response
DSMB	Data Safety Monitoring Board
ECG	Electrocardiogram
FSH	Follicle stimulating hormone
GI	Gastrointestinal
Gy	Gray
Hgb	Hemoglobin
HIV	Human Immunodeficiency Virus
HPF	High-power field
HRT	Hormone replacement therapy
HTN	Hypertensions
IMRT	Intensity-modulated radiation therapy
IRB	Institutional Review Board
irRECIST	Immune-related response evaluation criteria in solid tumors
IV	Intravenous
LLN	Lower limit of normal
MCPyV	Merkel cell polyomavirus
OS	Overall survival
PLT	Platelet
PD	Progressive diseased
PFS	Progression free survival
PR	Partial response
RECIST	Response evaluation criteria in solid tumors
RR	Response rate
SAE	Serious adverse event
SBRT	Stereotactic body radiation therapy
SD	Stable disease
SOC	Standard of Care
TTP	Time to progression
ULN	Upper limit of normal
UNK	Unknown
WBC	White blood cell
WHO	World Health Organization
WOCBP	Women of childbearing potential

1. OBJECTIVES

1.1. Primary Objective

The primary objectives of this study are to assess 1) the safety and 2) efficacy of combining Anti-PD-1/PD-L1 blockade with palliative radiation therapy in patients with Stage IV Merkel Cell Carcinoma. Efficacy for the primary objective will be tumor response rates (CR, PR, SD, irCR, irPR, irSD) at both irradiated and unirradiated sites.

1.2. Secondary Objectives

Assessment of Overall Survival and disease control rate/duration of response (CR, PR, SD, irCR, irPR, irSD)

1.3. Exploratory Objective

Optional exploratory objectives (dependent upon funding) will include mutational burden/MSI analysis, measurement of polyomavirus in the blood, immune response assays at baseline, 2 weeks (± 1 weeks) and 8 weeks (± 1 weeks) after radiation therapy, and possible tumor biopsy studies.

2. BACKGROUND

2.1 Merkel Cell Carcinoma and Immunotherapy

Merkel Cell Carcinoma is a rare and aggressive skin cancer for which much is written although rigorous trials are lacking (1). In general, many patients still die of advanced stage IV disease having a 5 year survival of 13.5%. (2) Recent approval of the checkpoint inhibitor, avelumab, likely improves this dismal outcome, but to some extent increasing awareness and diagnosis of this entity may also be contributing to improved outcomes. Swedish Cancer Registry incidence shows a doubling in close to 20 years. (3) Besides, avelumab other recent breakthroughs in knowledge include the association in some cases of the DNA virus, known as Merkel Cell Polyomavirus with the disease. (4) Historically, patients with localized disease are treated with surgery with or without radiation. Although these treatments can be associated with good outcomes, the strength of data for the exact delivery of such treatments is still weak due to the lack of good controlled studies. In addition, many patients develop metastatic disease with chemotherapy being the major treatment option in previous decades. Again, the data is of low quality, but the lack of long-term responders suggests only minor benefit. Further improvements are clearly needed, including controlled studies and increased research on new ideas to improve upon current therapy.

Immunological aspects of Merkel Cell include, in some patients, viral association, and increasing incidence in the setting of immune suppression such as with transplant (5). Regardless of immunological profile, the recent approval of avelumab, an anti-PDL-1 monoclonal antibody (6) has led to much renewed interest in systemic therapy in general and immunotherapy specifically. Although the trial was not randomized, it did suggest benefit and showed long term efficacy in some patients. Further strengthening the efficacy of avelumab was its use after chemotherapy. Pembrolizumab (Keytruda), an anti-PD1 antibody, has also been studied with evidence of long-term clinical benefit. (7), and was approved by the FDA in December 2018.

Given our knowledge of efficacy of radiation (8) for local control and smaller benefits of chemotherapy for the treatment of Merkel cell carcinoma, combination therapy with checkpoint inhibitors and radiation therapy makes sense. The immunological nature and

radiosensitivity of Merkel cell carcinoma and encouraging results to date with PD-1/PD-L1 axis inhibition, provide a compelling rationale for the study of the combination of checkpoint inhibition and radiation therapy as a means of inducing a clinically meaningful anti-Merkel cell carcinoma immune response. We and others have studied this approach in melanoma (9, 10) and other diseases, with impressive results in a subset of patients. This continues to be a very active and promising area of clinical investigation. Given the features of Merkel cell carcinoma discussed above, we hypothesize that it is likely that this approach will be beneficial in Merkel cell carcinoma as well.

2.2 Anti-PD-L1/PD-1 Inhibition in Merkel Cell Carcinoma

Avelumab (Bavencio) is a programmed death ligand-1 (PD-L1) blocking antibody approved for 1) metastatic Merkel Cell Carcinoma (MCC) and 2) locally advanced and metastatic urothelial cancer. It is dosed at 800 mg IV every 2 weeks. Until progression of disease or unacceptable toxicity. The most common AEs (20% and above) in MCC patients were fatigue, musculoskeletal pain, diarrhea, nausea, infusion-related reactions, rash, decreased appetite and peripheral edema. The most common AEs in urothelial carcinoma patients were fatigue, infusion reactions, musculoskeletal pain, nausea, decreased appetite and urinary tract infections. In a study of 88 MCC patients, the overall response rate was 33 % with 11.4% complete responses, and duration of response ranging from 2.8-23.3+ months.

Pembrolizumab (Keytruda) is a PD-1 blocking antibody, approved for multiple indications, and most recently in December 2018, approved for recurrent locally advanced or metastatic MCC. The approval was based on the Phase II CITN-09/KEYNOTE-017 trial in which pembrolizumab resulted in an Overall Response Rate (ORR) of 56%, PR rate of 32% and CR rate of 24% in patients who had not previously received systemic therapy for their advanced disease. An additional 10% had stable disease. In this multicenter, single arm trial, 50 treatment naïve patients were treated with pembrolizumab at 2 mg/kg every 3 weeks. 86% of patients had metastatic disease and 64% were positive for Merkel cell polyomavirus (MCPyV). At a median follow up of 14.9 months the median duration of response (DOR) was not reached. Among the 28 patients with response, 96% had a DOR of at least 6 months, and 54% had a DOR of 12 months or more. Both Progression Free Survival (PFS) and median Overall Survival (OS) with pembrolizumab were higher than historical data for chemotherapy controls. The median time to response was 2.8 months, with most responses occurring by 12 weeks. Responses were observed regardless of Merkel cell polyomavirus (MCPyV) status, with an ORR of 59% in MCPyV-positive patients and 53% among MCPyV-negative patients. The most common AEs of pembrolizumab reported in at least 20% of patients who received single-agent pembrolizumab were fatigue, musculoskeletal pain, decreased appetite, pruritus, diarrhea, nausea, rash, pyrexia, cough, dyspnea, constipation, pain and abdominal pain. Overall, 96% of patients experienced all-grade treatment-related AEs, with 14% of patients discontinuing treatment due to treatment-related AEs. Grade 3 and above treatment-related AEs were reported for 28%, and there was one treatment-related death in this study.

Additional information regarding pembrolizumab (e.g. PK, route of elimination, metabolism, etc.) can be found in the package insert.

2.3 Rationale

The underlying hypothesis for this study is that local radiation therapy (RT) can be safely used in combination with PD-1/PD-L1 blockade. This combination therapy may have the potential

to enhance the induction of systemic anti-Merkel cell carcinoma immune responses, which will inhibit growth and kill Merkel cell tumor cells in sites of established metastases outside of the local radiation therapy field.

This is a single institution study of pembrolizumab combined with palliative radiation therapy in patients with metastatic Merkel cell carcinoma. Palliative treatment means treatment to shrink a tumor, slow its growth or control symptoms. Patients must require radiation therapy for palliation of symptoms or to prevent local progression of disease and associated complications and/or symptoms from metastases.

Radiation therapy (RT) is commonly used to palliate sites of metastatic disease. Radiation can locally kill Merkel carcinoma cells and result in the release of tumor antigens in close proximity to antigen presenting cells (APC) in tumors, which could help to initiate an anti-tumor immune response. The combination of RT with PD-1/PD-L1 blockade, which inhibits co-inhibitory signaling in between T cells and tumor, may result in enhanced anti-tumor responses that result in greater tumor burden reduction systemically.

2.4 Study Design and Duration

This is a single institution, single arm, open-label, Phase II treatment study to evaluate the safety and efficacy of palliative radiation therapy combined with pembrolizumab as a means of providing for PD-1/PD-L1 checkpoint blockade in patients with metastatic Merkel Cell Carcinoma as either first line therapy or upon progression on prior therapy.

In this study, pembrolizumab will be administered at 200 mg IV every 3 weeks as standard of care as approved by the FDA. Palliative radiation therapy will be given between the first and second cycles of immunotherapy.

Subject participation in this study comprises the following time periods:

- Screening
 - Screening assesses the subject's eligibility to participate as determined by the inclusion/exclusion criteria.
 - Screening labs and ECOG Performance Status must be completed within 4 weeks of confirmation of eligibility. Imaging must be completed within 4 weeks of confirmation of eligibility and within 6 weeks of starting pembrolizumab therapy.
 - Eligibility must be confirmed within 28 days of signing the informed consent form.

- Pembrolizumab
 - Patients will receive pembrolizumab as a single agent administered 200 mg as standard of care intravenously every 3 weeks until progression or unacceptable toxicity.
 - Laboratory evaluations must be performed and the results examined before administration of each dose.
 - As durable disease stabilization and/or objective tumor response can be seen after early progression before Week 12, it is recommended that, in the absence of dose-limiting toxicities (e.g., serious AEs), immunotherapy be administered over

the initial 12 weeks even in the setting of apparent clinical progression, providing the subject's performance status remains stable.

- All subjects, including those who may have discontinued treatment for drug-related AEs and/or who have evidence of clinical progression, should obtain a tumor assessment 3 weeks (± 1 week) after the last dose of pembrolizumab.

- Based on clinical experience in ongoing and completed immunotherapy studies, the following recommendations apply for subject management in light of the tumor assessment taken 3 weeks (± 1 week) after the last dose of pembrolizumab:

- The appearance of new lesions in subjects with other stable or shrinking baseline tumor burden may be experiencing clinical benefit and should continue on treatment before alternative anti-cancer agents are considered. These subjects can be seen to have continued tumor shrinkage in subsequent imaging.
- As long as overall tumor burden is stable or decreasing, subjects can remain in treatment, even in the presence of new lesions, at the discretion of the treating physician.
- Clinical progression warranting alternative anti-cancer treatment should be considered in subjects whose overall tumor burden appears to be substantially increased and/or in subjects whose performance status is decreased.

- Follow-Up

- Subjects with SD, PR or CR will continue receiving pembrolizumab every 3 weeks per standard of care. After the last dose of pembrolizumab, subjects will enter Follow-Up. Efficacy assessments for these subjects are per standard of care.

- Survival Follow-Up (Post Study Follow-Up)

- Subjects who are no longer receiving pembrolizumab due to unacceptable toxicity (e.g., refractory Grade > 3 AEs), disease progression, investigator judgment, or study closure are managed in survival follow-up.

- If possible, subjects will be contacted or medical records reviewed every 6 months (± 2 weeks) for 5 years after the last dose of pembrolizumab to evaluate survival status.

2.5 Correlative Studies Background

Correlative studies will be performed if/when funding for them becomes available.

- Mutational burden/MSI - has been associated with response to checkpoint inhibitors in other solid tumor types (e.g. melanoma), and we would look at this to see if there is an association between this endpoint and response in MCC in our study
- Measurement of MC polyomavirus - to look for an association between this endpoint and response
- Immune Response Assays - to look for potential immune response biomarkers associated with response - e.g. may include Luminex for 51 cytokines testing in serum or plasma, ELISA for MHC class 1 polypeptide-related sequence A (MYCA) and MHC class 1 polypeptide-related sequence B (MYCB) in serum or plasma, immunophenotyping including myeloid-derived suppressor cells (MDSC) and gamma/delta T cells, mass cytometry or CyTOF ICS with phorbol 12-myristate 13-acetate (PMA) + ionomycin stimulation (global immunocompetence assay)

Because of relatively small patient numbers we will be looking for trends/correlations with response.

3. PARTICIPANT SELECTION AND ENROLLMENT PROCEDURES

3.1 Inclusion Criteria

- 3.1.1 Histologically confirmed metastatic or locally advanced Merkel Cell Carcinoma (includes in-transit or bilateral bulky disease) with at least two distinct sites of disease.
- 3.1.2 Subjects with brain metastases and/or carcinomatous meningitis are eligible providing they are neurologically stable (if systemic steroids are required, subjects should be stable on the lowest clinically effective dose, as steroids may interfere with the activity of immunotherapy if administered at the time of the first Anti-PD-1/PD-L1 dose.)
- 3.1.3 Must be at least 14 days since treatment for MCC, and recovered (baseline or residual non ir Grade 1 toxicity or ir Grade 2 toxicity at the investigator's discretion, see section 4.1.1) from any clinically significant toxicity experienced during treatment before the first dose of on study pembrolizumab therapy.
- 3.1.4 Eastern Cooperative Oncology Group (ECOG) performance status of 0 to 2.
- 3.1.5 Life expectancy of ≥ 16 weeks.
- 3.1.6 Subjects must have measurable disease according to RECIST v1.1, and have baseline (screening/baseline) radiographic images, (e.g. CT, PET CT or MRI brain, chest, abdomen, pelvis, to be determined by the attending physician) within 4 weeks of confirmation of eligibility and within 6 weeks before the initiation of on study pembrolizumab therapy.
- 3.1.7 Required values for initial laboratory tests:
 - WBC: $\geq 2000/\mu\text{L}$ ($\sim 2 \times 10^9/\text{L}$)
 - ANC: $\geq 1000/\mu\text{L}$ ($\sim 1 \times 10^9/\text{L}$)
 - Platelets: $\geq 50 \times 10^3/\mu\text{L}$ ($\sim 50 \times 10^9/\text{L}$)
 - Hemoglobin: ≥ 8 g/dL
 - Calculated creatinine clearance (eGFR) greater than 30mL/min
 - AST/ALT: Less than 2.5 x ULN for subjects without liver metastasis, less than 5 times ULN for liver metastases
 - Bilirubin: less than 3.0 x ULN (except for subjects with Gilbert's Syndrome, who must have a total bilirubin of less than 3.0 mg/dL)
 - Non-clinically significant laboratory abnormalities such as lipase elevation would not be an exclusion.
- 3.1.8 No known active or chronic infection with HIV, Hepatitis B, or Hepatitis C, or active infection requiring systemic antibiotics. Testing for the above is not required unless clinically suspected.

- 3.1.9 At least one measurable site of disease (≥ 10 mm as per RECIST v1.1 except for lymph nodes that must be 15 mm or greater on the short axis) outside of the planned palliative radiation therapy field.
- 3.1.10 Require radiation therapy for palliation of symptoms or to prevent local progression of disease and associated complications and/or symptoms from metastases.
- 3.1.11 Men and women, at least 18 years of age.
- 3.1.12 Women of childbearing potential (WOCBP) must be using an adequate method of contraception to avoid pregnancy throughout the study [and for up to 26 weeks after the last dose of investigational product] in such a manner that the risk of pregnancy is minimized.

WOCBP include any female who has experienced menarche and who has not undergone successful surgical sterilization (hysterectomy, bilateral tubal ligation, or bilateral oophorectomy) or is not postmenopausal. Post-menopausal is defined as:

- Amenorrhea ≥ 12 consecutive months without another cause, or
- For women with irregular menstrual periods and on hormone replacement therapy (HRT), a documented serum follicle stimulating hormone (FSH) level > 35 mIU/mL

Women who are using oral contraceptives, other hormonal contraceptives (vaginal products, skin patches, or implanted or injectable products), or mechanical products such as an intrauterine device or barrier methods (diaphragm, condoms, spermicides) to prevent pregnancy, or are practicing abstinence or where their partner is sterile (e.g., vasectomy) should be considered to be of childbearing potential. WOCBP must have a negative serum or urine pregnancy test (minimum sensitivity 25 IU/L or equivalent units of HCG) within 1 week prior to the start of investigational product.

- 3.1.13 Men of fathering potential must be using an adequate method of contraception to avoid conception throughout the study [and for up to 26 weeks after the last dose of investigational product] in such a manner that the risk of pregnancy is minimized.

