4. TREATMENT PLAN

Screening/Baseline Visit

The following tests and examinations must be performed and the eligibility criteria satisfied before treatment may begin:

- Histologic diagnosis of Merkel Cell Carcinoma
- Demographics and medical history
- Measurements of weight, height, temperature, pulse, respiratory rate, and resting systolic and diastolic blood pressure
- Complete physical examination
- ECOG Performance Status
- Clinical laboratory tests:
 - Hematology: hemoglobin, hematocrit, CBC counts with differential (including absolute lymphocyte count) and direct platelet count
 - Serum Chemistry: albumin, serum alkaline phosphatase, SGOT (AST)/SGPT (ALT), total bilirubin, calcium, creatinine, glucose, lactate dehydrogenase (LDH), total protein, urea nitrogen (BUN), electrolytes (including sodium, potassium, chloride, and bicarbonate), TSH w/Reflex FT4
 - Urinalysis:
 - Gross examination including specific gravity, protein, glucose, and blood
 - Optional microscopic examination including WBC/HPF, RBC/HPF and any additional findings
- Optional Blood sample obtained for investigational immune response assays
- Chest radiography unless baseline CT scan was performed
- Electrocardiogram
- Relevant baseline radiographic images (e.g. brain, chest, abdomen, pelvis, and bone scans with the exact imaging studies utilized determined by the attending physician) within 6 weeks of initiation of anti-PD-1/PD-L1

- Current medications
- Baseline review of symptoms
- Pregnancy test
- Optional Tumor biopsy

Treatment Visits

The day subjects receive the first dose of pembrolizumab therapy will define Day 1. Subjects are required to have blood collected and chemistry labs analyzed up to 1 week prior to each dose of pembrolizumab. Investigators or an assigned medical professional must review liver function tests from the predosing labs and ensure the results meet dosing requirements prior to authorizing administration of each dose of pembrolizumab.

Subjects will receive a single dose of pembrolizumab as standard of care with 200mg IV every 3 weeks (with a -3 and +7-days window) until disease progression or unacceptable toxicity occurs.

During this treatment phase, the following procedures will be performed within 1 week of each scheduled visit:

- Pregnancy test for WOCBP, required within 6 weeks before first dose of pembrolizumab, then optional as clinically indicated for ongoing doses

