9. STUDY CALENDAR

Visits	Pre Study Visit	Treatment Visits					End of Treatment Visit	Follow Up Visit	Post Study Follow Up
	Wk 0	Wk 1 ^h	Btw Wk 1-3	Wk 4	Wk 7	Wk 10	3 Wks after last dose of Pembrolizumab	Every 3, 6M, or at yr 5 from last dose of Pembrolizumab	Upon progression or unacceptable symptomatology
Investigational Agent ^a		X		X	X	X			
Radiation Therapy ^b			X						
Informed consent	X								
Inclusion/Exclusion Criteria	X								

Demographics	X								
Medical history	X								
Physical Exam	X	X		X	X	X	X	X	
Concurrent meds ^c	X	X		X	X	X	X	X	
Vital signs	X	X		X	X	X	X	X	
ECOG Performance status	X	X		X	X	X	X	X	
ECG	X								
Chest Radiography	X								
Adverse event evaluation		X		X	X	X	X	X	
Tumor measurements	X						X	X	
CBC w/diff	X	X		X	X	X	X	X	
Pregnancy Test ^d (Urine or Serum)	X	X		X	X	X			
Hemoglobin	X	X		X	X	X	X	X	
Hematocrit	X	X		X	X	X	X	X	
Metabolic panel, comp	X	X		X	X	X	X	X	
LDH total serum plasma	X	X		X	X	X	X	X	
Urinalysis Macro (Opt Micro)	X								
TSH w/Reflex FT4 ^e	X						X	X	
Optional Immune Response and Polyomavirus Tests ^f	X		X	X		X	X		
Optional Tumor Biopsy ^f	X		X	X	X	X	X	X	
Survival Follow Up ^g									X

a: Investigational Agent- pembrolizumab 200 mg infused SOC every 3 weeks

b: Radiation Therapy- 1-2 sites of disease, delivered between the first and second cycles of pembrolizumab, 9 Gy X 3 (27 Gy in 3 fractions), or 4-6 Gy X 5 (20-30 Gy in 5 fractions)

c: Concurrent meds will be collected until the patient goes off study due to disease progression or change in therapy for Merkel cell carcinoma or for 2 years of continuing response

d: Pregnancy test conducted and negative result confirmed before administration of pembrolizumab in women with the potential to become pregnant, pregnancy test is required ≤ 6 weeks before first dose of pembrolizumab and optional as clinically indicated for ongoing doses

e: Assessed at week 13 for patients who continue pembrolizumab past week 10

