3.1.1.2	
Women of childbearing potential (WOCBP) must be using an adequate method of contraception to avoid pregnancy throughout the study [and for up to 26 weeks after the last dose of investigational product] in such a manner that the risk of pregnancy is minimized.
 
WOCBP include any female who has experienced menarche and who has not undergone successful surgical sterilization (hysterectomy, bilateral tubal ligation, or bilateral oophorectomy) or is not postmenopausal. Postmenopausal is defined as:
 
 • Amenorrhea \geq 12 consecutive months without another cause, or 	6 week before therapy		Preg. Test Date:			

	
 For women with irregular menstrual periods and on hormone replacement therapy (HRT), a documented serum follicle stimulating hormone (FSH) level > 35 mIU/mL 
Women who are using oral contraceptives, other hormonal contraceptives (vaginal products, skin patches, or implanted or injectable products), or mechanical products such as an intrauterine device or barrier methods (diaphragm, condoms, spermicides) to prevent pregnancy, or are practicing abstinence or where their partner is sterile (e.g., vasectomy) should be considered to be of childbearing potential. WOCBP must have a negative serum or urine pregnancy test (minimum sensitivity 25 IU/L or equivalent units of HCG) within 6 week prior to the start of investigational product.
						
3.1.1.3	Men of fathering potential must be using an adequate method of contraception to avoid conception throughout the study [and for up to 26 weeks after the last dose of investigational product] in such a manner that the risk of pregnancy is minimized.	NA					

	Conditions for Patient Ineligibility						
3. 2. 1	WOCBP who are unwilling or unable to use an acceptable method to avoid pregnancy for the entire study and for up to 26 weeks after the last dose of investigational product.	NA					
3. 2. 2	Women who are breastfeeding.	NA					
3. 2. 3	WOCBP with a positive pregnancy test within 6 weeks before enrollment.	6 week before therapy		Preg. Test Date:			

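### Inclusion criterion 3.1.12 requires a negative pregnancy test within 1 week before study drug, but its checklist copy, the treatment plan and the study calendar allow 6 weeks

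*Combined protocol and SAP*

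**What the plan says.** Section 3.1, criterion 3.1.12, asks for a negative serum or urine test "within 1 week prior to the start of investigational product".

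Four other places give a different window:

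- **Appendix 2, row 3.1.12.** The sentence from the criterion is repeated, but reads "within 6 week prior to the start of investigational product". The row's window column agrees with that: "6 week before therapy".
- **Section 4, Treatment Visits.** "Pregnancy test for WOCBP, required within 6 weeks before first dose of pembrolizumab, then optional as clinically indicated for ongoing doses".
- **Section 9, note d.** "pregnancy test is required ≤ 6 weeks before first dose of pembrolizumab".
- **Section 9, note h, item 4.** The list of requirements before the first dose gives 6 weeks for the pregnancy test. Item 5 of the same list gives 1 week for labs and liver function tests.

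Two further provisions matter. Section 4 opens its screening list by requiring "the eligibility criteria satisfied before treatment may begin". It also already requires "blood collected and chemistry labs analyzed up to 1 week prior to each dose of pembrolizumab".

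**The concern.** A single eligibility criterion carries two time limits that differ sixfold, and the looser one sits in the documents staff work from. Appendix 2 says the checklist must be completed before registration and that eligibility must be verified by the coordinator, the treating physician and an independent reviewer. All three would be checking against 6 weeks. Note h, the pre-dose list, also says 6 weeks. Staff could follow both lists exactly and still give pembrolizumab to a woman who does not meet the criterion in section 3.1.

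What is at stake is participant safety and clean eligibility. The older the accepted test, the more time there is for a pregnancy to begin after it and go unnoticed at the first dose.

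**Working it through.** The plan states no figure to reproduce. The check compares the windows and uses simple day counts.

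**Same anchor.** The calendar lists pembrolizumab as the investigational agent, and radiation comes after its first dose. The start of investigational product, the start of therapy and the first pembrolizumab dose are therefore the same day, so the windows can be compared directly.

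| Place | Limit on test age at dose 1 |
|---|---|
| Section 3.1, criterion 3.1.12 | 1 week = 7 days |
| Appendix 2, row 3.1.12 (text and window column) | 6 weeks = 42 days |
| Section 4, Treatment Visits bullet | 42 days |
| Section 9, note d | 42 days |
| Section 9, note h, item 4 | 42 days |

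Counting the checklist row once, four places say 6 weeks and one says 1 week.

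**Zone of conflict.** A test 0 to 7 days old satisfies all five places. A test 8 to 42 days old satisfies four and fails 3.1.12. That is 42 − 7 = 35 possible test ages, in days. A test older than 42 days fails everywhere.

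**Can the schedule produce such test ages?** Section 2.4 requires imaging within 28 days of confirmed eligibility and within 42 days of starting pembrolizumab. Taking imaging as done on or before the day of confirmation:

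- imaging 28 days before confirmation: dose 1 can follow confirmation by up to 42 − 28 = 14 days;
- imaging on the day of confirmation: up to 42 − 0 = 42 days.

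Both exceed 7 days. If the checklist is completed when eligibility is confirmed (an assumption), any test recorded on it is already too old for 3.1.12 whenever dose 1 comes more than 7 days later.

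**Does other text restore the 1-week limit?**

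- The Treatment Visits list opens with a general window of 1 week around each visit, but the pregnancy bullet under it states its own 6-week window.
- The calendar marks a pregnancy test at Wk 1, but note d, attached to that row, accepts a test up to 6 weeks old. Its requirement for a negative result before dosing does not set the age of the test.
- Exclusion 3.2.3, "WOCBP with a positive pregnancy test within 6 weeks before enrollment", concerns a positive result and counts from enrollment. It does not set the age of the negative test at dose 1.

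None of these removes the conflict.

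**The case against.** The strongest reply is that 6 weeks is the intended rule and 3.1.12 is simply un-updated text. Four places agree on 6 weeks. Note h puts a 6-week pregnancy test directly beside 1-week labs, which looks deliberate. The checklist must be complete before registration, and a 1-week limit tied to dose 1 cannot always be met by then. This stands as a reason to ask the sponsor which window was meant. It does not remove the defect: whichever window is right, at least one place is wrong as written, and no text explains the difference.

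A second reply is that the practical risk is low. A test within 7 days satisfies every place. Contraception is mandatory (3.1.12, 3.2.1), note d requires a negative result before dosing, and section 5.1.1.3 stops pembrolizumab on pregnancy. A pregnancy can also be missed after a 7-day-old test, so the difference is one of degree. All of this is correct and limits the size of the point.

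A reader might infer that the documents establish 1 week as the true rule, because section 4 requires the criteria to be met before treatment. They do not go that far. The checklist presents its 6-week text as the same criterion, and nothing sets an order of precedence. A reader might also infer that ineligible or pregnant women were treated; the documents contain no such information.

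**Conclusion.** The inconsistency is real and should be corrected. A woman of childbearing potential last tested 8 to 42 days before dose 1 passes the checklist and the pre-dose list but fails 3.1.12 as it stands in section 3.1. The comparison of windows rests only on the written text. The likelihood of such test ages rests also on the assumption that the checklist is completed when eligibility is confirmed.

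The number of women affected cannot be derived from the documents. The matter concerns eligibility and safety only; the response endpoints, the analyses and the sample of 30 are untouched. The documents do not show which window was intended, so preferring 1 week is a safety judgement.

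**What to change.** State one window and make every place match it.

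**Safer choice: keep 3.1.12 as written.** Change 6 weeks to 1 week in:

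1. the pregnancy-test bullet under Treatment Visits in section 4;
2. notes d and h (item 4) of the section 9 calendar;
3. the text and the window column of row 3.1.12 in Appendix 2, with a note in that row that, if dose 1 falls more than 7 days after registration, the 1-week test is confirmed at the pre-dose check in note h.

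The test can be done with the labs already due within 1 week before dosing. The cost is text edits at the next amendment and checklist version, one repeat urine or serum test for a woman whose earlier test is more than 7 days old, and in some cases one item confirmed at the pre-dose check instead of at registration.

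**Alternative: if the sponsor intended 6 weeks.** The only edit needed is to change 1 week to 6 weeks in criterion 3.1.12 of section 3.1. This is simpler, but it relaxes a written safety criterion, so the sponsor should make that choice explicitly.
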